7.1.3.5 Screening for Hepatitis B Virus (HBV)

Each subject must undergo a screening for hepatitis B virus (HBV), which at a minimum includes testing for HBV surface antigen (HBsAg), HBV surface antibody (anti-HBs), and HBV core antibody total (anti-HBc total), and demonstrate to be eligible based on the following results:

- Subjects who test **positive** for surface antigen (HBsAg+) **are not eligible** for this trial, regardless of the results of other hepatitis B tests.
- Subjects who test **negative** for surface antigen (HBsAg-) and test **positive** for core antibody (anti-HBc+) **and** surface antibody (anti-HBs+) **are eligible** for this trial.
- Subjects who test **positive only** for **surface antibody** (anti-HBs+) **are eligible** for this trial.
- Subjects who test **positive only** for **core antibody** (anti-HBc+) must undergo further testing for hepatitis B deoxyribonucleic acid (HBV DNA test). If the HBV DNA test is **positive**, the subject **is not eligible** for this trial. If the HBV DNA test is **negative**, the subject **is eligible** for this trial. In the event the HBV DNA test cannot be performed, the subject **is not eligible** for this trial.

Action	Hepatitis B Surface Antigen(HBsAg)	Hepatitis B Surface Antibody(anti-HBs)	Hepatitis B Core Antibody(anti-HBc Total)
Exclude	+	- or +	- or +
Include	-	+	+
Include	-	+	-
Include	-	-	-
Require Hepatitis B viral DNA (HBV DNA) testing*	-	-	+
* If HBV DNA is detectable or there is evidence of chronic liver disease, exclude from clinical trial. If the HBV DNA test is negative, the subject is eligible for this trial. In the event the HBV DNA test cannot be performed, the subject is not eligible for this trial.			

7.1.3.6 Pharmacokinetic (PK) and Immunogenicity Evaluations

7.1.3.6.1 Blood Collection for Plasma MK-8259

Analyses for MK-8259 (golimumab) concentration will be performed using a validated method. It is important to accurately record the date/time of administration of the trial medication as well as the date/time that each sample was collected for PK analysis. Sample collection, storage and shipment instructions for plasma samples will be provided in the central operations/laboratory manual.

7.1.3.6.2 Blood Collection for Antibodies to Golimumab (MK-8259)

Serum samples will be used to evaluate the antibodies to golimumab. Instructions for the collection, handling, and shipping of blood samples are provided in the Laboratory manual.

7.1.3.7 Future Biomedical Research

The following specimens are to be obtained as part of Future Biomedical Research:

- DNA for future research

7.1.3.8 Planned Genetic Analysis Sample Collection

Sample collection, storage and shipment instructions for planned genetic analysis samples will be provided in the central operations/laboratory manual.

7.1.4 Other Procedures

7.1.4.1 Withdrawal/Discontinuation

Subjects who discontinue/withdraw from treatment prior to completion of the treatment should be encouraged to continue to be followed for all remaining study visits.

When a subject discontinues/withdraws from participation in the trial, all applicable activities scheduled for the discontinuation visit should be performed at the time of discontinuation. Any adverse events which are present at the time of discontinuation/withdrawal should be followed in accordance with the safety requirements outlined in Section 7.2 - Assessing and Recording Adverse Events and subjects will have a safety follow-up telephone call 3 months after their last dose of trial medication.

7.1.4.1.1 Withdrawal From Future Biomedical Research

Subjects may withdraw their consent for Future Biomedical Research and have their specimens and all derivatives destroyed. Subjects may withdraw consent at any time by contacting the principal investigator for the main trial. If medical records for the main trial are still available, the investigator will contact the Sponsor using the designated mailbox ([contact]), and a form will be provided by the Sponsor to obtain appropriate information to complete specimen withdrawal. Subsequently, the subject's specimens will be removed from the biorepository and be destroyed. A letter will be sent from the Sponsor to the investigator confirming the destruction. It is the responsibility of the investigator to inform the subject of completion of destruction. Any analyses in progress at the time of request for destruction or already performed prior to the request being received by the Sponsor will continue to be used as part of the overall research trial data and results. No new analyses would be generated after the request is received.

In the event that the medical records for the main trial are no longer available (e.g., if the investigator is no longer required by regulatory authorities to retain the main trial records) or the specimens have been completely anonymized, there will no longer be a link between the subject's personal information and their specimens. In this situation, the request for specimen destruction cannot be processed.

7.1.4.2 Blinding/Unblinding

When the investigator or sub-investigator needs to identify the drug used by a subject and the dosage administered in case of emergency e.g., the occurrence of serious adverse experiences, he/she will contact the emergency unblinding call center by telephone and make a request for emergency unblinding. As requested by the investigator or sub-investigator the emergency unblinding call center will provide the information to him/her promptly and report unblinding to the sponsor. The emergency unblinding call center will make a record promptly however, the investigator or sub-investigator must enter the intensity of the adverse experiences observed, their relation to study drug, the reason thereof, etc., in the medical chart etc., before unblinding is performed.

Additionally, the investigator must go into the IVRS system and perform the unblind in the IVRS system to update drug disposition. In the event that the emergency unblinding call center is not available for a given site in this trial, IVRS/IWRS should be used for emergency unblinding in the event that this is required for subject safety.

In the event that unblinding has occurred, the circumstances around the unblinding (e.g., date and reason) must be documented promptly, and the Sponsor Clinical Director notified as soon as possible. Only the principal investigator or delegate and the respective subject's code should be unblinded. Trial site personnel and Sponsor personnel directly associated with the conduct of the trial should not be unblinded.

7.1.4.3 Calibration of Critical Equipment

The investigator or qualified designee has the responsibility to ensure that any critical device or instrument used for a clinical evaluation/test during a clinical trial that provides important information about inclusion/exclusion criteria and/or safety or efficacy parameters shall be suitably calibrated and maintained to ensure that the data obtained is reliable and/or reproducible. Documentation of equipment calibration must be retained as source documentation at the trial site.

Critical Equipment for this trial includes:

- Weight scale
- Centrifuge

7.1.5 Visit Requirements

Visit requirements are outlined in Section 6.0 - Trial Flow Chart. Specific procedure-related details are provided above in Section 7.1 - Trial Procedures.

7.1.5.1 Screening and Baseline Eligibility (Visit 1 and Visit 2)

All screening procedures (including MRI) required to assess subjects' eligibility for the trial should be completed within the 2 months (60 days) prior to administration of the first dose of open-label golimumab at Visit 2. IVRS/IWRS should be used beginning with the Screening visit and ending with completion/discontinuation visit.

Subjects in this study may be rescreened once prior to receiving open-label golimumab, with prior approval by the Sponsor trial physician. If a subject is rescreened, the same screening number must be used.

When it is confirmed at Baseline (Visit 2 or “Month 0”) that a subject is eligible to enter Period 1 (to receive open-label golimumab), the subject should be assigned an allocation number using the IVRS/IWRS. Refer to the IVRS/IWRS user manual for additional details.

7.1.5.2 Month-4 Clinic Visit (Visit 10)

At Month 4 (Visit 10), all subjects will be assessed for clinical response based on BASDAI score. Subjects who attain a clinical response by Month 4 (or earlier) will continue to receive golimumab monthly during Period 1. A clinical response is defined as a BASDAI score improvement of ≥ 2 (on a NRS from 0 to 10) or $\geq 50\%$ improvement, when determined relative to the score at Month 0. Subjects who have not attained a clinical response by Visit 10 will be discontinued from the study and will have a safety follow-up telephone call 3 months after their last dose of trial medication.

7.1.5.3 Month-7 Clinic Visit (Visit 16)

At Month 7 (Visit 16), all assessments listed in Trial Flow Chart - Section 6.0 will be performed including those required to calculate ASDAS: BASDAI, PGD_N and CRP testing. Trial medication will not be administered at Visit 16. Once the Visit-16 CRP test result is available (from the central laboratory), the site will determine the ASDAS in order to assess for inactive disease status (defined as ASDAS <1.3).

- Subjects who show ASDAS <1.3 at Visit 16 are to continue in the trial and complete Period 1. Sites will schedule only these eligible subjects for the next clinic visit (Visit 17, which should occur about 2 to 7 days after Visit 16) to dispense open-label golimumab to complete Period 1.
- Subjects who show ASDAS ≥ 1.3 at Visit 16 will be discontinued from the trial. Sites will call these subjects for an unscheduled visit to perform procedures that are required at the Discontinuation (DC) visit but were not performed at Visit 16. These procedures include obtaining vital signs, GADI, routine laboratory blood testing, and pregnancy test (if required). These subjects will have a safety follow-up telephone call 3 months after their final dose of trial medication.

7.1.5.4 Month-10 Clinic Visit (Visit 23)

After approximately 10 months of open-label therapy (with the final dose of open-label golimumab during Period 1 administered at Month 9), assessments at Visit 23 will be performed, including those required to calculate the ASDAS: BASDAI, PGD_N and CRP testing. Trial medication will not be administered at Visit 23. Once the Visit-23 CRP test result is available (from the central laboratory), the site will determine the ASDAS in order to assess for inactive disease status (defined as ASDAS <1.3).

- Subjects who show ASDAS <1.3 at Visit 23 are eligible to enter Period 2 and receive double-blind treatment. Sites will schedule only these eligible subjects for the next clinic visit (Visit 24, which should occur about 2 to 7 days after Visit 23). At Visit 24, subjects will receive their initial dose of blinded trial medication and thereafter will continue monthly administration during Period 2. The next clinic visit (Visit 28) should be scheduled about 2 months after Visit 24.
- Subjects who show ASDAS ≥ 1.3 at Visit 23 will be discontinued from the trial. These subjects will have a safety follow-up telephone call 3 months after their final dose of trial medication.

7.1.5.5 Unscheduled Visit(s) to Confirm a “Flare” during Period 2

Evaluations by Telephone Contact(s) during Period 2

As obtained (via electronic device) during Period 2, if the BASDAI score is increased by ≥ 2 (on the 0 to 10 NRS) compared to Month 10 (Visit 23), then sites will call subjects to also obtain a Patient Global Disease assessment (on Numeric scale) (PGD_N) score. (Subjects may also contact the clinic if they believe a “flare” is occurring, regardless of their BASDAI score. In this situation, sites will call the subject to obtain both the BASDAI and the PGD_N. Similarly, if the BASDAI increase by ≥ 2 is observed at a regularly scheduled clinic visit, then this situation can initiate the additional assessments to confirm a “flare”.) Using these values obtained for BASDAI and PGD_N, sites will also use the last available CRP value (i.e., the CRP result from the previous clinic visit) to determine the ASDAS. Based on this ASDAS, there are 2 possible decisions:

- (1) If this ASDAS shows absolute score <2.1 and post-withdrawal increase (i.e., change from Visit 23) of <1.1, then this assessment is not consistent with a “flare”. The subject is expected to continue the double-blind trial-medication administration and the scheduled clinic visits without change.
- (2) If this ASDAS shows absolute score ≥ 2.1 and/or post-withdrawal increase of ≥ 1.1 , then the subject will be asked to come to the clinic, for an unscheduled visit, for an additional assessment for confirmation of a “flare”. This additional assessment should occur within ideally 2 to 10 days (but no more than 3 weeks); or this assessment can occur at a previously scheduled clinic visit, if the timing fits within ideally 2 to 10 days (but no more than 3 weeks) from the first assessment.

Evaluations during a Clinic Visit needed to Confirm a “Flare”

During a “flare-confirmation” visit, evaluations required to calculate ASDAS (BASDAI, PGD_N, CRP testing) will be performed. Using the BASDAI and PGD_N obtained *during* this “flare-confirmation” visit (and understanding that the result of the CRP test collected during this visit is not yet available), the investigator will determine the ASDAS using the BASDAI and PGD_N scores and assuming the minimum value of CRP that is defined for use in calculating ASDAS, which is CRP = 2 mg/L [8]. This ASDAS determines the decision among the following:

- (1) If the ASDAS shows absolute score ≥ 2.1 and/or post-withdrawal increase (i.e., change from Visit 23) of ≥ 1.1 , then this will confirm that a “flare” is occurring. The subject will begin re-treatment with open-label golimumab, which is then to be continued monthly through the end of Period 2. The next clinic visit should be scheduled about 2 months after the first dose of re-treatment with open-label golimumab.
- (2) If the ASDAS shows absolute score < 2.1 and post-withdrawal increase of < 1.1 , the subject will not be treated with the open-label golimumab at this unscheduled visit. However, when the CRP value becomes available from the sample collected at this “flare-confirmation” visit, the investigator must then re-calculate the ASDAS.
 - (2a) If the re-calculation of ASDAS (now using the new CRP value) shows absolute score ≥ 2.1 and/or post-withdrawal increase of ≥ 1.1 , then this will confirm that a “flare” is occurring. Once it is confirmed that a “flare” is occurring, the subject will be asked to return for a second unscheduled visit in order to begin re-treatment with open-label golimumab, which should then continue monthly through the end of Period 2. The next clinic visit should be scheduled about 2 months after the first dose of re-treatment with open-label golimumab.
 - (2b) If the re-calculation of ASDAS (now using the new CRP value) shows absolute score < 2.1 and post-withdrawal increase of < 1.1 , then this second assessment does not confirm a “flare”. The subject is expected to continue the double-blind trial-medication administration and the scheduled clinic visits without change.

Note: In a scenario in which the BASDAI increase by ≥ 2 is observed at a regularly scheduled clinic visit and the “flare-confirmation” visit is then scheduled within ideally 2 to 10 days (but no more than 3 weeks), the CRP obtained at the regularly scheduled clinic visit can be used in the confirmatory determination of the ASDAS during the “flare-confirmation” visit. In this scenario, decisions (1) or (2b) above will pertain.

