At Month 10 (Visit 23; see also Trial Flow Chart – Section 6.1), evaluations are performed to calculate ASDAS. Subjects who have attained inactive disease status (defined as ASDAS < 1.3) at both Months 7 and 10 of open-label treatment are eligible to enter the double-blind withdrawal period (see Section 7.1.5.4 for more details); only these subjects are to be scheduled for the next clinic visit (Visit 24), which begins Period 2. Eligible subjects undergo stratified randomization in a 1:1:1 ratio to one of the following 3 treatment arms: 1) treatment-withdrawal (i.e., monthly injections of matching-placebo for golimumab), 2) golimumab QM (i.e., a full-treatment regimen, per approved labeling), or 3) golimumab Q2M (i.e., a reduced-treatment regimen, via monthly injections that alternate between golimumab and matching-placebo for golimumab). Strata are defined by the presence or absence of elevated CRP (> 6.0 mg/L vs. ≤ 6.0 mg/L) at the Screening visit. Eligible subjects receive their initial dose of blinded trial medication during Visit 24. Subjects who do not have inactive disease at Visit 23 do not enter Period 2; these subjects are discontinued from the study (and will have a safety follow-up telephone call 3 months after their last dose of trial medication).

Over the course of 12 months during Period 2, subjects return to the trial site for evaluation, including laboratory testing, approximately every 2 months (starting from the initial dose of double-blind trial medication). Subjects also continue to complete the BASDAI questionnaire twice monthly in order to rate disease activity. If there is an increase of ≥ 2 (on the 0 to 10 NRS) in BASDAI score compared to Month 10 (Visit 23), the trial site calls the subject to initiate a full evaluation of whether a “flare” (indicative of increased disease activity) is occurring; assessments include information obtained over the phone and/or at an unscheduled visit. A “flare” is defined by ASDAS collected at 2 consecutive assessments that both show absolute score ≥ 2.1 and/or post-withdrawal increase (i.e., change from Visit 23) of ≥ 1.1 (see Section 7.1.5.5 for details on confirming a “flare”).

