4.2.3 Rationale for Endpoints

4.2.3.1 Efficacy Endpoints

Inactive disease status and a disease “flare” in this trial are defined using the ASDAS. The ASDAS was developed by ASAS as an index for disease activity measurement in axial SpA that includes subjective measures (rated by the subject) and objective measure (CRP) to create a well-balanced index [3]. This score combines 5 disease activity variables that have only partial overlap, resulting in one single score with better validity, enhanced discriminative capacity, and improved sensitivity to change as compared with single-item variables. Cutoffs to identify “disease activity states” and “response criteria” using the ASDAS were first identified in 2011 [4]. This trial will use the cutoffs defined by ASAS:

- Level of ASDAS to identify subjects with inactive disease: ASDAS < 1.3 ;
- Level of ASDAS to identify subjects with a “flare”: ASDAS ≥ 2.1 (which defines high disease activity) and/or a change in ASDAS by ≥ 1.1 (which is considered a clinically important change).

The BASDAI score, which combines 6 questions that are self-assessed by subjects, is used to define a clinical response in this trial, both to open-label treatment with golimumab and to re-treatment with open-label golimumab after a “flare”. Clinical response is defined as a BASDAI score improvement by ≥ 2 (on a 0 to 10 scale) and/or score improvement by $\geq 50\%$. This definition of a “responder” is from the ASAS recommendations for use of TNF inhibitors in subjects with Axial SpA [2]. To assess the response to open-label golimumab, the response is compared with the BASDAI score at Month 0; to assess the response to re-treatment, the response is compared with the mean of the 2 BASDAI scores obtained when the “flare” was diagnosed.

To characterize the symptoms and signs of nr-axSpA in subjects treated with golimumab or withdrawn from golimumab, other secondary endpoints will be assessed in this trial. These include ASAS20, ASAS40, BASDAI50, and ASAS Partial Remission. All of these endpoints have been studied in many previous studies of axial SpA. Of note, in the GO-AHEAD

(P07642) trial in subjects with nr-axSpA, golimumab was shown to be superior to placebo for each of these endpoints [1].

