- b. Remote completion of the BASDAI questionnaire by subjects, twice monthly, using an electronic device.
- c. If the subject discontinued from the trial during Period 2, trial medication will not be administered at the DC clinic visit.
- d. If subjects report an increase of ≥ 2 BASDAI score compared with Month 10 (Visit 23), site is to call subject to obtain Patient Global Disease Assessment, and then use the CRP value from the previous clinic visit to calculate ASDAS. See Section 7.1.5.4 for more details.
- e. If “flare” (defined as ASDAS absolute score ≥ 2.1 and/or post-withdrawal increase (i.e., change from Visit 23) of ≥ 1.1 at 2 consecutive visits) is confirmed *during* a “flare confirmation” visit (based on the BASDAI and PGD_N obtained at that visit), subject will begin re-treatment with open-label golimumab for the confirmed “flare” at that visit. Clinic visits are then to be scheduled every 2 months from the date of the initial re-treatment with open-label golimumab
- f. If “flare” is confirmed *after* a “flare confirmation” visit (based on the CRP result as eventually received from that visit), then the subject is asked to return to the clinic to begin re-treatment with open-label golimumab for the “flare”. Clinic visits are then to be scheduled every 2 months from the initial re-treatment with open-label golimumab.
- g. The safety follow-up phone call is made approximately 3 months after the last dose of trial medication.
- h. When it is confirmed at Visit 23 that a subject is eligible for Period 2, site to call IVRS/IWRS to randomize the subject into Period 2 (Double-blind) prior to administering the trial medication; assign trial medication at all clinic visits; update the subject status at V48/DC visit.
- i. During Period 2, site personnel will administer the trial medication (± 5 days) during clinic visits. If subjects are self-injecting, the monthly dose to be administered (± 5 days) between clinic visits will be dispensed for subjects to self-inject at home.
- j. PEs would include a full skin assessment and would be directed to evaluate signs and symptoms of potential AEs assessment.
- k. If local law requires more frequent pregnancy testing, the site will perform the assessments as per local requirement
- l. At all visits, samples MUST be collected BEFORE the administration of trial medication.
- m. The same sample will be used for detection of antibodies to golimumab and neutralizing antibody analysis.

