8.4.1 Efficacy Endpoints

8.4.1.1 Primary Efficacy Endpoint

The primary efficacy endpoint for this trial is the proportion of subjects without a disease activity “flare” during up to 12 months in Period 2 (in subjects who attained inactive disease status after receiving open-label golimumab in Period 1).

A “flare” is defined as ASDAS at two consecutive visits that both show *either* absolute score ≥ 2.1 *or* post-withdrawal increase (i.e., change from Visit 23) of ≥ 1.1 .

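### Flare is defined on ASDAS alone, but an ASDAS crossing at a scheduled Period 2 visit does not open confirmation or re-treatment unless BASDAI has also risen by 2 or the subject calls

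*Combined protocol and SAP*

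**What the plan says.** **Definition.** In Section 2.1 a flare is "defined by ASDAS collected at 2 consecutive assessments that both show absolute score" of at least 2.1 and/or a rise of at least 1.1 from Visit 23. In Section 8.4.1.1 it "is defined as ASDAS at two consecutive visits that both show" either condition. Neither section sets a BASDAI condition.

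**Routes into confirmation (Section 7.1.5.5).** There are three:
- a BASDAI rise of at least 2 from Visit 23, recorded remotely;
- the subject contacting the site, whatever the BASDAI;
- the same BASDAI rise seen at a clinic visit: "Similarly, if the BASDAI increase by ≥ 2 is observed at a regularly scheduled clinic visit, then this situation can initiate the additional assessments".

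Footnote d of Section 6.2 repeats the BASDAI condition: "If subjects report an increase of ≥ 2 BASDAI score compared with Month 10 (Visit 23), site is to call subject". Section 2.1 does the same.

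**Data at scheduled visits.** The Section 6.2 flow chart marks BASDAI, patient global (PGD_N) and CRP at Visits 28, 32, 36, 40, 44 and 48, about 2 months apart, with three remote BASDAI scores in each interval.

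**Orders to calculate ASDAS.** For Visit 16, Section 7.1.5.3 says that once CRP is back "the site will determine the ASDAS in order to assess for inactive disease status". Section 7.1.5.4 does the same for Visit 23. No such instruction exists for the scheduled Period 2 visits.

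**At the confirmation visit.** The site first calculates ASDAS "assuming the minimum value of CRP that is defined for use in calculating ASDAS", that is 2 mg/L. If this does not confirm a flare, it recalculates when the new CRP arrives. A note for subjects whose BASDAI rise was seen at a scheduled visit allows a shortcut: "the CRP obtained at the regularly scheduled clinic visit can be used in the confirmatory determination of the ASDAS".

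**The concern.** Section 4.2.3.1 gives the reason for choosing ASDAS: it "includes subjective measures (rated by the subject) and objective measure (CRP) to create a well-balanced index". BASDAI contains neither CRP nor patient global. Gating an ASDAS endpoint on BASDAI removes those two components from the decision to look for a flare, even at visits where both are measured.

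Two things are at stake. The first is care. Subjects are randomised to withdrawal or reduction of an effective drug, and Section 4.3 offers the 2-monthly clinic visits as a safeguard alongside the self-ratings. For a crossing with a BASDAI rise below 2, the clinic visit opens nothing. The subject stays on blinded therapy, possibly placebo, although the components in hand already meet the trial's flare level.

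The second is ascertainment. A single crossing of this kind becomes a flare only if a later assessment also qualifies. Without another trigger, that assessment is the next scheduled visit. After Visit 48 there is none.

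**Working it through.** **1. Inputs from the plan.**
- BASDAI = 0.2 × (Q1 + Q2 + Q3 + Q4 + 0.5 × [Q5 + Q6]) (Section 8.4.3.1).
- ASDAS = 0.12 × Q2 + 0.06 × Q6 + 0.11 × PGD_N + 0.07 × Q3 + 0.58 × ln(CRP + 1), with CRP below 2 mg/L set to 2 (Section 8.4.3.2).
- Entry to Period 2 requires ASDAS below 1.3 at Visit 23.

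**2. ASDAS rise needed.** From a Visit 23 ASDAS of 1.29, reaching 2.1 takes 2.1 − 1.29 = 0.81. From 1.0 or below, the 1.1 rise applies. With Visit 23 CRP at 2 or less, the lowest possible ASDAS is 0.58 × ln 3 = 0.64, so the range is 0.81 to 1.1. With Visit 23 CRP at 5, the lowest is 0.58 × ln 6 = 1.04, so 2.1 is reached first and the range is 0.81 to 1.06.

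**3. A symptom rise just short of the trigger.** Let all BASDAI items and PGD_N rise by 2, except Q5 by 1.
- BASDAI rise = 0.2 × (8 + 0.5 × 3) = 1.9, so no trigger.
- ASDAS rise from these items = 2 × (0.12 + 0.06 + 0.11 + 0.07) = 2 × 0.36 = 0.72.

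**4. CRP needed to cross.** CRP = (base + 1) × exp[(need − item rise)/0.58] − 1, where base is the Visit 23 CRP.

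| Symptom change | Item rise | Base CRP ≤2 mg/L | Base CRP 5 mg/L |
|---|---|---|---|
| BASDAI +1.9, as in step 3 | 0.72 | 2.5 to 4.8 | 6.0 to 9.8 |
| None | 0 | 11 to 19 | 23 to 36 |

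For example, 3 × exp[(1.1 − 0.72)/0.58] − 1 = 4.8. Visit 23 CRP can be as high as exp(1.3/0.58) − 1 = 8.4 mg/L with ASDAS still below 1.3, so the base matters.

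**5. A crossing with CRP unchanged.** PGD_N +6 and back pain (Q2) +4 give 0.11 × 6 + 0.12 × 4 = 1.14 on ASDAS and 0.2 × 4 = 0.8 on BASDAI.

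**6. Effect on power.** The plan's figure comes first: 75% vs 40% without flare, 38 per arm, two-sided 0.05. The pooled normal approximation gives 88.6% against 88% in Table 7. Exact unstratified Miettinen-Nurminen power is 88.4%. Now suppose a share f of flares is never confirmed and counts as no flare. The documents give no value for f, so these are assumptions (exact power):

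| f | 80% vs 30%, both arms | 80% vs 30%, placebo only | 75% vs 40%, both arms | 75% vs 40%, placebo only |
|---|---|---|---|---|
| 1% | 99.6% | 99.6% | 87.9% | 87.3% |
| 7% | 99.1% | 98.6% | 84.0% | 79.3% |

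For example, 7% of placebo flares missed moves 40% without flare to 40 + 0.07 × 60 = 44.2%.

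**The case against.** The strongest reply is that the endpoint itself is not gated. Section 8.4.1.1 has no BASDAI condition, the components are in the database, and two successive scheduled crossings count at analysis. This stands. A reader might infer that the primary analysis counts only flares that BASDAI opened, or that power is materially lost. The documents support neither: the definition is ASDAS-only, and the power losses above rest on assumed miss rates.

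A reader might also infer that times to first flare are systematically late. Section 8.6.1 does not say which of the two assessments dates a flare. If the first one does, two qualifying visits cause no delay in the recorded time.

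Next, other routes soften the gap. BASDAI is scored about every two weeks, subjects may call at any score, and Section 7.1 lets the investigator add unscheduled procedures when clinically necessary. Someone with PGD_N up by 6 may well call. This limits how often the full 2-month wait occurs, but none of these routes is triggered by ASDAS.

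Third, the low CRP values depend on the base. At a Visit 23 CRP of 5 mg/L, the near-miss case needs 6.0 to 9.8 mg/L. It would be wrong to say in general that crossings occur below the trial's 6.0 mg/L cut-off for elevated CRP.

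Finally, Section 4.3 describes the risk of withdrawal mainly as worsening symptoms, so a symptom-led trigger between visits is defensible. It is a weaker argument at clinic visits, where CRP is drawn anyway.

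**Conclusion.** The concern holds as a gap between the flare definition and the procedure that detects flares. An ASDAS crossing at a scheduled Period 2 visit, with BASDAI up by less than 2 and no call, opens neither confirmation nor re-treatment. The wait is up to about 2 months unless a remote score, a call or investigator discretion intervenes. A first such crossing at Visit 48 cannot be confirmed.

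The main consequences are later re-treatment and less complete flare ascertainment. The formulas show that such crossings are possible at moderate values, but the frequency is unknown and no miss rate is claimed. The effect on the primary comparison is probably small at the planned 80% vs 30%. This is a change the sponsor should make because it is cheap and applies the plan's own definition; it does not invalidate the primary analysis.

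**What to change.** Amend Section 7.1.5.5, footnote d of Section 6.2 and the matching text of Section 2.1:

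- At each scheduled Period 2 visit, including Visit 48, the site calculates ASDAS when that visit's CRP is back. If ASDAS is at least 2.1 and/or up at least 1.1 from Visit 23, it starts the existing confirmation visit, regardless of BASDAI.
- Keep the 3-week limit and aim for about day 10. A blinded dose is given at the scheduled visit, and Section 2.1 requires at least 10 days before open-label golimumab.
- Keep the BASDAI and self-call triggers.
- Keep the CRP reuse note for subjects whose BASDAI rose by at least 2. A reader might want it removed so that one CRP is not used twice, but that would slow re-treatment for symptomatic subjects. Where only ASDAS opened confirmation, use the CRP drawn at the confirmation visit under decisions (1) to (2b).
- State that a Visit 48 crossing confirmed within the window is a Period 2 flare and receives the three-dose course in Section 2.1.

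**Cost.** The data, the calculation and the visit type already exist. There will be some extra confirmation visits, a few after Visit 48. Because decision (1) assumes CRP of 2 mg/L, CRP-driven cases will often need the second visit under (2a). Some subjects will move earlier to open-label golimumab with little symptom worsening.

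A Visit 48 flare with re-treatment from day 10 gives about 22.3 + 2 (to the third dose) + 3 (to the safety call) + 2 (screening) = 29.3 months of participation. With every window at its limit it is 29.9 to 30.2, against the 30 months in Section 2.1. The upper figure assumes 7 days for the second visit.

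Flares with a small BASDAI rise can rarely meet the re-treatment response, which needs a BASDAI improvement of at least 2 points or 50%. Show that secondary endpoint also by whether BASDAI had risen by at least 2 at flare.
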